## 6.3. Inclusion Criteria

This study attempts to prove the concept that patients who would never be treated with anti-Her-2 compounds can indeed be considered for this option. Specific information regarding warnings, precautions, contraindications, adverse events, and other pertinent

information on the investigational product that may impact subject eligibility is provided in the latest version of the lapatinib Investigator's Brochure or product labels.

Subjects eligible for enrolment in the study must meet all of the following criteria:

- 1. Signed written informed consent
- 2. Female patients, age  $\geq 18$  years
- 3. Histologically confirmed diagnosis of HER-2 negative (i.e. no gene amplification by FISH or IHC 2+ and no amplification by FISH or IHC 0/1+) infiltrating primary breast cancer.
- 4. Evidence of EGFR positive circulating tumour cells or HER-2 positive (≥50% CTCs or FISH positive) in a peripheral blood sample taken at screening visit.
- 5. Metastatic disease with at least one measurable lesion as per RECIST criteria classification [Therasse, 2000]
- 6. No brain metastasis requiring local therapy. Stable or asymptomatic subjects are allowed.
- 7. Availability of tumour block or at least six unstained 4  $\mu$  sections of the primary tumour to be sent to the central lab after eligibility confirmation for HER-2 central testing by FISH.
- 8. Eastern Cooperative Oncology Group (ECOG) score for performance status 0 to 3 (Appendix 1)
- 9. Life expectancy > 12 weeks
- 10. Adequate baseline organ function at screening visit:
  - Hematologic function:
    - ANC  $\geq$  1,000 / mm^3,
    - PLT  $\geq$  100,000 / mm^3,
    - $Hb \ge 10g / dL$  (after transfusion if needed)
  - Hepatic function:
    - GOT/GPT/alkaline phosphatase ≤ 3 ULN without liver metastases or ≤ 5 ULN if documented liver metastases;
    - total bilirubin: ≤1.5 ULN unless due to Gilbert's syndrome
  - Renal function:
    - serum creatinine ≤ 2.0mg/dL or Calculated Creatinine Clearance ≥ 25mL/min (Appendix 2)
- 11. Normal left ventricular ejection fraction (LVEF) by echocardiogram or MUGA.
- 12. Negative serum pregnancy test (only in childbearing potential female)
- 13. Patients with reproductive potential needs consistent and correct use of adequate non-hormonal methods of birth control (barrier methods or intrauterine device)

- 14. Previous treatment with anthracyclines and/or taxanes in the neo-adjuvant, adjuvant or advanced setting

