## 6.4. Exclusion Criteria

Subjects meeting any of the following criteria must not be enrolled in the study:

- 1. Any unstable systemic disease including active infections, significant cardiovascular disease, as well as myocardial infarction within the previous year, any significant hepatic (current active hepatic or biliary disease [with exception of patients with Gilbert's syndrome, asymptomatic gallstones, liver metastases or stable chronic liver disease per investigator assessment]), renal or metabolic disease, metabolic dysfunction, physical examination finding, or clinical laboratory finding that contraindicates the use of study medication or that might affect the interpretation of the results or render the patient at high risk from treatment complications.
- 2. Pregnant or lactating women
- 3. Dementia, altered mental status, or any psychiatric condition that could prohibit the understanding or rendering of informed consent
- 4. Lack of physical integrity of the upper gastrointestinal (GI) tract, poor absorption of the GI tract or inability to take oral medication
- 5. Other co-existing malignancy or malignancies within the last 5 years with the exception of basal cell carcinoma or in-situ carcinoma
- 6. Concurrent anti-cancer therapies (chemo or hormonal therapy) other than study drug
- 7. Concurrent treatment with an investigational agent or participation in any investigational drug study within 4 weeks preceding treatment start
- 8. Concurrent radiotherapy to the only target lesion. Concurrent bisphosphonates are allowed as long as this therapy has started before patient receives study medication.
- 9. Previous treatment with anti HER-2 or anti-EGFR therapies
- 10. Protocol specified treatment regimens that would be inappropriate for the management of the subject (See also concomitant medication Section 7.9).

Refer to Appendix 4 for additional exclusion criteria for patients who participate in the PET substudy.

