## 7.3.2. Liver Chemistry Stopping and Follow Up Criteria

## 7.3.2.1. Liver Chemistry Stopping Criteria

Liver chemistry stopping and follow up criteria have been designed to assure subject safety and evaluate liver event etiology. All subjects who meet liver chemistry criteria requiring permanent discontinuation of investigational product must continue to be followed for the study assessments and procedures as defined in Section 8. Study Assessments and Procedures and at the time points indicated in the Time & Events Table 8 in Section 8. Study Assessments and Procedures.

If a subject experiences ALT  $>3 \times$  ULN and total bilirubin  $>2.0 \times$  ULN (>35% direct; bilirubin fractionation required\*), then the following actions must be taken:

- immediately and permanently discontinue investigational product;
- complete the SAE data collection tool, the liver event CRF, and the liver imaging and/or liver biopsy CRFs, if these tests are performed;
- in addition to the liver event follow up assessments defined in Section 7.3.2.2 Liver Chemistry Follow-up Criteria below, the following are suggested: specialist or hepatology consultation; anti-nuclear antibody, anti-smooth muscle antibody, and Type 1 anti-liver kidney microsomal antibodies; and liver imaging and/or liver biopsy to evaluate liver disease;
- promptly report the event to GSK within 24 hours of learning its occurrence (refer to Section 9.7.3. Prompt Reporting of Serious Adverse Events and other Events to GSK for guidance on prompt reporting to GSK);
- monitor every week until liver chemistries resolve, stabilize or return to within baseline values;
- do not re-challenge with investigational product.

\***NOTE**: bilirubin fractionation should be performed if testing is available. If testing is unavailable and a subject meets the criterion of total bilirubin  $>2.0 \times ULN$ , then the aforementioned actions must still be performed.

If a subject experiences:

- ALT >8  $\times$  ULN or
- ALT >5 × ULN persisting for ≥2 weeks : retest within 3 days from the first occurrence and then weekly to determine if ALT elevation persists or
- ALT >3 × ULN with signs or symptoms of hepatitis or hypersensitivity (the appearance or worsening of fatigue, nausea, vomiting, right upper quadrant pain or tenderness, fever, rash, or eosinophilia),

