#### GM2007/00215/03

#### CONFIDENTIAL

then hold investigational product for 2 weeks, repeat liver chemistry testing in 2 weeks, and then call the Medical Monitor to discuss the possibility of re-challenging with investigational product.

If the treatment is exhibiting efficacy **and** the subject wants to continue for potential benefit of lapatinib therapy after being informed of the results of liver chemistry testing, then the investigational product may be re-started at the reduced dose agreed upon by the investigator and the Medical Monitor. The liver event CRF should be completed and liver chemistries and aforementioned signs and symptoms should be monitored at a minimum of every 2 weeks until resolution, stabilization, or a return to baseline values, at which point monitoring should be continued per protocol.

If a subject experiences ALT >3 × ULN **but** <5 × ULN **and** total bilirubin  $\leq$ 2 × ULN, without signs or symptoms of hepatitis or hypersensitivity, **and** who can be monitored weekly, then the following actions should be taken:

- continue investigational product;
- monitor weekly until liver chemistries resolve, stabilize, or return to within baseline, then monitor liver chemistries as per protocol assessment schedule;
  - if ALT >3 and  $< 5 \times$  ULN for > 4 weeks, discontinue the treatment;
- if at any time this subject meets any of the aforementioned liver chemistry stopping criteria, then proceed as described above.

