## 8.1. Critical Screening Assessments

All patients eligible for screening must sign an informed consent for the study before any study-related procedures are performed.

The screening period can least up to 28 days before first study drug administration.

The required observations are:

- Demography: date of birth, race,
- Medical an Therapy history
- Concomitant Medications
- Disease History: details of malignancy date of diagnosis, primary tumour histology, cancer stage, HER -2, EGFR and hormonal receptors status on primary tumours, previous cancer treatment for adjuvant and metastatic setting, ongoing toxicities related to previous treatment,

- Vital Signs: blood pressure, pulse rate, body temperature, body weight and height
- Physical Examination
- ECOG: it is recommended, wherever possible, that a patient's performance status will be assessed by the same person throughout the study.
- 12 lead ECG
- ECHO or MUGA
- Hematology, Chemestry (ANC, PLT, Hb, Total bilirubin, serum creatinine or Calculated Creatinine, ALT (SGPT), AST (SGOT), LDH, alkaline phosphatase)
- For all childbearing potential female a negative serum pregnancy test must be obtained within 14 days before starting Lapatinib treatment
- For the Italian sites (stratum 1) Evaluation of HER-2 status on CTCs: 2 blood samples will be sent to the central laboratory (Prato hospital) for CTC evaluation.
- For the UK sites (stratum 2) Evaluation of EGFR status on CTCs: 2 blood samples will be sent to the central laboratory (Hammersmith hospital) for CTC evaluation

For patients resulting CTC HER-2 + or EGFR+, a Paraffin-embedded tumour block or at least six unstained 4  $\mu$  sections of primary tumour will be collected and sent to the central laboratory. Italian samples should be sent to Prato hospital and UK samples should be sent to Hammersmith hospital.

**NOTE:** All laboratory assessments will be performed locally. Lab normal ranges must be provided to GSK before study start. For the purposes of this study, examinations or laboratory analyses that must have results provided by the day of the scheduled visit and recorded in CRF.

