# 11.3. Data Analysis Considerations

# 11.3.1. Analysis Populations

## **Per Protocol Population**

The per protocol population will be defined as all subject fulfilling major entry inclusion/exclusion criteria who received at least 75 % of study drug doses up to first tumour assessment at week 12, and have at least one efficacy measurement available on the primary outcome. Subjects who progress prior to the week 12 assessment will also be included in this analysis. This population will be used for the primary objective of the study and for all efficacy analyses and summaries.

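### Entry allows ALT up to 5 x ULN with liver metastases, but Section 7.3.2.1 stops drug for ALT between 3 and 5 x ULN lasting over 4 weeks and does not exempt a value present at entry

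*Protocol*

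**What the plan says.** Criterion 10 in Section 6.3 requires "GOT/GPT/alkaline phosphatase ≤ 3 ULN without liver metastases or ≤ 5 ULN if documented liver metastases" and "total bilirubin: ≤1.5 ULN unless due to Gilbert's syndrome". GPT and ALT are the same test: Section 8.1 lists "ALT (SGPT), AST (SGOT), LDH, alkaline phosphatase". Exclusion criterion 1 in Section 6.4 keeps these subjects eligible, because its exceptions include "asymptomatic gallstones, liver metastases or stable chronic liver disease per investigator assessment".

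Section 7.3.2.1, added by Amendment 03, has two rules that reach the same ALT range:

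- **Hold.** One trigger for a two-week hold is "ALT >3 × ULN with signs or symptoms of hepatitis or hypersensitivity". The listed symptoms include new or worse fatigue, nausea and rash.
- **Continue, then stop.** This tier covers ALT above 3 and below 5 x ULN with bilirubin at or below 2 x ULN, no such symptoms, and weekly monitoring possible. Drug continues and the instruction is to "monitor weekly until liver chemistries resolve, stabilize, or return to within baseline, then monitor liver chemistries as per protocol assessment schedule". A sub-item then says that ALT in that range "ULN for > 4 weeks, discontinue the treatment".

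The first scheduled tumour evaluation is at week 12, with a window of 7 days either way (Section 8.3.1). The per-protocol population in Section 11.3.1 serves the primary objective. It takes subjects who "received at least 75 % of study drug doses up to first tumour assessment at week 12" and also those who progress before that assessment. Section 6.5 says that subjects who discontinue prematurely are not replaced.

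**The concern.** For subjects with documented liver metastases, criterion 10 opens an entry range above 3 and up to 5 x ULN. Almost all of that range is the range in which Section 7.3.2.1 stops treatment after 4 weeks. The stopping limits are multiples of ULN. They are not tied to the subject's own starting value and do not mention liver metastases. The protocol can write baseline-relative rules when it wants them: the LVEF rules in Section 7.3.1 are framed relative to baseline.

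Within the tier, the two lines also pull apart for a stable subject. One returns her to routine monitoring once her values are stable or at baseline; the other takes her off drug after 4 weeks in range. Two sites could treat the same patient differently, and both could cite the protocol.

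At stake is who stays on drug until the first scan, and who is in the primary analysis of a trial with 16 to 31 subjects per stratum.

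**Working it through.** **1. Overlap of the ranges**

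| ALT at entry, liver metastases documented | Criterion 10 | Section 7.3.2.1 if the value does not change |
|---|---|---|
| up to 3 x ULN | eligible | no ALT limit met |
| above 3, below 5 x ULN, no symptoms | eligible | stop after more than 4 weeks |
| above 3, up to 5 x ULN, new or worse symptoms | eligible | hold for 2 weeks |
| exactly 5 x ULN, no symptoms | eligible | in neither the below-5 nor the above-5 tier |

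The bilirubin entry limit of 1.5 x ULN places an entrant inside the tier's condition of at most 2 x ULN, Gilbert's syndrome aside. Section 9.5 lists rash and nausea as expected side effects, so the hold trigger is not remote for a subject who starts above 3 x ULN.

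**2. Timing and dose share.** Assumptions: the 4-week clock starts at first dose, dosing is daily, and the denominator is the 84 days to week 12.

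- Threshold: 0.75 x 84 = 63 days.
- Stop at day 29: 29/84 = 34.5%. Stop at day 35: 35/84 = 41.7%.
- Scan at day 77: 29/77 = 37.7% and 35/77 = 45.5%. Scan at day 91: 29/91 = 31.9% and 35/91 = 38.5%.

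Every case is below 75%. A single two-week hold followed at once by a restart would leave 70/84 = 83.3%, above the threshold. It is therefore the 4-week stop that removes the subject from the per-protocol set.

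**3. The design as written.** With X1 ~ Bin(16, p) and X2 ~ Bin(15, p):

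- Reject = P(X1=0) + P(X1=1)P(X2≤1) + P(X1=2)P(X2=0)
- Inconclusive = P(X1=1)P(X2=2) + P(X1=2)P(X2=1) + P(X1=3)P(X2=0)
- Accept = 1 - reject - inconclusive

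At p = 0.20:

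- Reject = 0.02815 + 0.01882 + 0.00743 = 0.0544
- Inconclusive = 0.02600 + 0.02785 + 0.00867 = 0.0625
- Accept = 0.8831

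At p = 0.05: accept 0.0647, reject 0.8152. Section 11.1 states a type I error of 10%, a type II error of 5%, and at least 80% for each correct decision. The rule meets these, except that rejection at 20% is 5.4%, marginally above 5%.

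**4. Illustration.** The protocol gives no share of subjects entering at 3 to 5 x ULN. Let a fraction f of all subjects be stopped for this reason, be counted, and be unable to respond. The effective rate is then 0.20 x (1 - f).

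| f (assumed) | effective rate | accept | reject |
|---|---|---|---|
| 0 | 0.20 | 0.8831 | 0.0544 |
| 5% | 0.19 | 0.8555 | 0.0686 |
| 10% | 0.18 | 0.8228 | 0.0862 |
| 15% | 0.17 | 0.7847 | 0.1077 |

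Now suppose instead that such subjects leave the per-protocol set, are not replaced, and the cut-offs stay the same. Losing 1, 2, 3 or 4 subjects in a stratum (the first two from stage 1) gives acceptance of 0.8649, 0.8441, 0.8265 or 0.8066 at a true 20% rate.

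**The case against.** **The limits may be meant for new rises.** The tier opens with what a subject experiences, and Section 2.2 explains the stopping rules in terms of changes in liver function. Section 7.3.2.1 does mention baseline, and the 4-week line is printed as a sub-item of the bullet that lets a stable subject return to routine monitoring. On that reading, a subject unchanged from entry is never stopped. The reading is possible, and the Appendix 5 algorithm figure, which might settle it, is not visible here. But in the text, baseline only ends the extra monitoring, and the discontinuation line carries no such qualifier. The ambiguity stands.

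**The group is narrow.** This is right. It needs documented liver metastases and entry ALT above 3 x ULN. The 4-week line covers only asymptomatic subjects with bilirubin at or below 2 x ULN who can be monitored weekly. It does not discontinue everyone between 3 and 5 x ULN. Nor is it impossible to obey both sections: a subject can be enrolled and then stopped.

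**Such a subject may still be scanned and counted.** This is also right. Table 8 schedules imaging at early withdrawal, and Section 7.3.2.1 keeps subjects who are permanently stopped under the liver criteria on study assessments. The Withdrawal paragraph of Section 11.5 includes subjects who leave treatment but not the study in all analyses, whatever the duration of treatment. That does not sit easily with the 75% rule. What is lost is drug exposure and, if the 75% rule governs, membership of the primary set. One cannot say that she had no chance to respond.

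**Two further inferences fail.** A reader might think that the Gilbert's exception in criterion 10 creates the same conflict. The bilirubin rule also requires ALT above 3 x ULN and more than 35% direct bilirubin, so trouble arises only with all of these together: Gilbert's, raised ALT and no fractionation. A reader might also think that unchanged entry values would inflate the reported liver harm. Section 9.1 keeps pre-existing conditions that do not worsen out of adverse events. Section 9.2 does the same for findings due to the underlying disease, unless they are worse than expected. Section 11.5.2 names no table of liver discontinuations.

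**Conclusion.** The conflict is in the current text and holds for one subgroup: subjects with documented liver metastases and entry ALT above 3 x ULN. Read literally, an unchanged, eligible value such as 4 x ULN ends treatment just after day 28, about 8 weeks before the scheduled scan. If Section 11.3.1 governs, the subject then leaves the primary set unless she progresses first. If the Withdrawal paragraph of Section 11.5 governs, she is counted after about a month of drug.

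The thresholds and the dose shares come from the protocol's own figures, given the clock and denominator assumed in step 2. The effect on the decision rule does not: the 5-15% shares have no source. The first table also treats every such subject as stopped and unable to respond, although some would fall below 3 x ULN, move to another tier or progress. It would be wrong to infer that the design misses its 80% target. Acceptance falls below 80% only at the assumed 15%.

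**What to change.** Reconcile criterion 10 in Section 6.3 with Section 7.3.2.1. State in Section 7.3.2.1 how both the hold and the 4-week limit apply to a subject whose ALT was already above 3 x ULN at entry, when the 4-week clock starts, and how the limit relates to the stable-or-baseline wording beside it. Bring Appendix 5 into line. Which passage changes is for the clinical team to decide. State also whether the 75% rule in Section 11.3.1 or the Withdrawal paragraph in Section 11.5 decides whether a subject stopped for this reason is in the primary analysis.

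The cost is wording in the next amendment, with no extra subjects, visits or tests. A split of liver discontinuations by entry ALT would be an optional detail for the statistical analysis plan.

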## 6.4. Exclusion Criteria

Subjects meeting any of the following criteria must not be enrolled in the study:

- 1. Any unstable systemic disease including active infections, significant cardiovascular disease, as well as myocardial infarction within the previous year, any significant hepatic (current active hepatic or biliary disease [with exception of patients with Gilbert's syndrome, asymptomatic gallstones, liver metastases or stable chronic liver disease per investigator assessment]), renal or metabolic disease, metabolic dysfunction, physical examination finding, or clinical laboratory finding that contraindicates the use of study medication or that might affect the interpretation of the results or render the patient at high risk from treatment complications.
- 2. Pregnant or lactating women
- 3. Dementia, altered mental status, or any psychiatric condition that could prohibit the understanding or rendering of informed consent
- 4. Lack of physical integrity of the upper gastrointestinal (GI) tract, poor absorption of the GI tract or inability to take oral medication
- 5. Other co-existing malignancy or malignancies within the last 5 years with the exception of basal cell carcinoma or in-situ carcinoma
- 6. Concurrent anti-cancer therapies (chemo or hormonal therapy) other than study drug
- 7. Concurrent treatment with an investigational agent or participation in any investigational drug study within 4 weeks preceding treatment start
- 8. Concurrent radiotherapy to the only target lesion. Concurrent bisphosphonates are allowed as long as this therapy has started before patient receives study medication.
- 9. Previous treatment with anti HER-2 or anti-EGFR therapies
- 10. Protocol specified treatment regimens that would be inappropriate for the management of the subject (See also concomitant medication Section 7.9).

Refer to Appendix 4 for additional exclusion criteria for patients who participate in the PET substudy.

## 6.5. Withdrawal Criteria

Treatment with investigational product should be discontinued if a subject experiences disease progression, unacceptable toxicities (as described Dose Adjustment, Modifications for Toxicities, Section 7.3), become pregnant, in the judgment of the investigator continuation of the treatment regimen is inappropriate for the clinical management of the subject or withdrawal of consent. In subjects presented with symptoms and signs of suggestive pneumonitis, lapatinib treatment should be withheld until diagnosis is confirmed. Patients diagnosed with pneumonitis possibly related to lapatinib should be removed from study.

## Subjects with an NCI CTC AE Grade 3 or 4 left ventricular systolic dysfunction or interstitial pneumonitis must be withdrawn from treatment.

The investigator should perform all the assessments as listed for the Early Withdrawal in Table 8. The reason for withdrawal from study treatment must be documented in CRF.

A follow up visit should be performed in 28 days after last dose administration.

Subjects who are prematurely discontinued from the study will be not replaced.

## 7. STUDY TREATMENTS

## 7.1. Investigational Product

Lapatinib ditosylate monohydrate tablets, 250 mg, are oval, biconvex, orange, filmcoated tablets that are embossed on one side with FG HLS. Tablets contain 410 mg of lapatinib Ditosylate Monohydrate, equivalent to 250 mg lapatinib free base per tablet. Refer to the Investigator's Brochure (IB) for information regarding the physical and chemical properties of the drug substance and list of excipients.

